10.3.5 Informed Consent and Research Authorization (HIPAA) Forms

Only patients who continue to meet study eligibility criteria will be allowed to continue to the enrollment phase.

10.4 Enrollment Assessments

10.4.1 Demographics

Demographics forms collect information about demographic characteristics of the study participant, including age, gender, cultural/ethnic group, education level, marital status, and type of insurance. This form is completed at enrollment only.

10.4.2 Locator Information Form

A locator form is used to obtain information to assist in finding study participants during the 90 day assessment period. The form collects contact information including the participant's current address, email address, and phone number. In an effort to facilitate locating participants if direct contact efforts are unsuccessful, address and phone number of family/friends who may know how to reach the participant are also collected. This information will be collected at enrollment. Locator information will not be used in data analysis.

10.4.13 Satisfaction Scale

A short 3 question satisfaction scale will be used to measure satisfaction with the screening and linkage process. This will be asked at enrollment and the 30, 60, and 90-day follow-up assessments.

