9.5 Follow-up

All follow-up assessments will be performed over the phone. Follow-up assessments will occur at 30, 60, and 90 days post enrollment.

Follow-up assessments will include:

- 1) Attitudes toward Pre-Exposure Prophylaxis Scale (APS) (Appendix 3)
- 2) Section 4 of ICAP "Screening for Substantial Risk of HIV" (Appendix 5)
- 3) Satisfaction questionnaire and qualitative assessment and visit specific satisfaction instrument (VSQ-9) (Appendix 6)
- 4) Adherence information measured by (1) self-report. Self-report will be assessed with the single measure Guidelines Regimen Information Program (GRIP) guide and questions on last dose and number of missed doses since prior follow-up. (Appendix 7)
- 5) CDC Sexual Behavior Questions (CSBQ) (Appendix 4)
- 6) STAR*D PRISE (Side-effect assessment)

Assessment of engagement in PrEP care at 30, 60, and 90 days post enrollment will be verified by direct contact with the treatment provider/program provided or by EMR review if the patient is linked within the Mount Sinai Health System. If the patient is receiving their PrEP care outside of the Mount Sinai Health System, a signed release authorization form will be sent.

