12.2. Study Procedures, Materials, and Potential Risks

Aim 1

Study Procedures: Patients found to be eligible for PrEP will be randomized to immediate PrEP (iPrEP) initiation using a 14-day starter pack or PrEP initiation in the outpatient clinic. Both groups will have facilitated linkage to care. Follow-up study visits will occur at 30, 60 and 90days post PrEP initiation. The 30, 60 and 90 day assessments will over the phone.

Effective Date: 4/20/2021

End Date: 3/18/2022

Risks: Aim 1 involves randomization to one of two different PrEP initiation programs. PrEP initiation carries risks that would be considered more than minimal. Patients in both groups will be prescribed tenofovir disoproxil fumarate (FTC/TDF) which will be used for women and transgender men or

emtricitabine/tenofovir alafenamide (FTC/TAF) which will be used for men and transgender women. Both of these medications are FDA approved and is being used for its intended purpose in the population for whom it is indicated. Known physical risks of emtricitabine/tenofovir disoproxil fumarate and emtricitabine/tenofovir alafenamide are impaired renal function, intolerable side effects including nausea, vomiting or diarrhea as well as hypersensitivity reaction and osteopenia with long term use. Patients will also be subject to the same psychological and privacy and confidentiality risks.

Sources of Data: Aim 1 data sources will come from the following

- 1) Socio-demographic questionnaires collected during screening and enrollment
- 2) Behavioral risk factor questionnaires collected at enrollment and 30, 60, and 90day follow-up
- 3) PrEP attitude and knowledge measures
- 4) Satisfaction questionnaires collected during enrollment and 30 , 60, and 90-day follow-up
- 5) Laboratory reports obtained from the patient's electronic medical record at enrollment and 30 and 90-day follow-up
- 6) Locator forms collected to obtain correct contact information collected at enrollment and 30 and 60 day follow up
- 7) VSQ-9 study visit questionnaires collected at 30 and 90-day follow-up
- 8) Adherence questionnaires collected at 30, 60, and 90-day follow-up
- 9) Facility follow-up questionnaire

Data for Aim 1 will be collected using a touch screen tablet and paper and pencil surveys administered by the RA. All data will be linked to the individual study participant but will be de-identified for analysis.

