21.0 Outcome measures

Secondary Outcome 1:	Retention in PrEP care at 30, 60, and 90 days post PrEP index visit
Type	Secondary
Time frame	30, 60 and 90 days
Description	# of patients retained in care at 30, 60 and 60-days post-PrEP initiation

Secondary Outcome 2: PrEP usage post PrEP index visit

Type	Secondary
Time frame	30, 60 and 90 days
Brief description	# of patients still using PrEP at 30 and 60-days post PrEP initiation

Secondary Outcome 3:	PrEP adherence at follow up post PrEP index visit
Type	Secondary
Time frame	30, 60, 90 days
Brief description	Level of adherence to PrEP at 30, 60, 90-days post PrEP initiation

Secondary Outcome 4:	Risk behavior post PrEP index visit
Type	Secondary
Time frame	30, 60, 90 days
Brief description	HIV risk behaviors at 30, 60, 90-days post PrEP initiation

Secondary Outcome 5:	STI diagnoses post PrEP index visit
Type	Secondary
Time frame	30, 60, 90 days
Brief description	# and type of STI diagnosed at 30 and 90-day post PrEP initiation visits

Secondary Outcome 6:	HIV infection
Type	Secondary
Time frame	90-days
Brief description	# of new HIV infections, if any, at 90-days post PrEP initiation

Secondary Outcome 7:	Program Satisfaction
Type	Secondary
Time frame	90-days
Brief description	Program satisfaction at 30, 60 and 90-day follow-up

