Appendix 2: Satisfaction Measure

Exposure Prophylaxis Provision in the Emergency Department (PrEPPED)
action and Acceptability Measures

all satisfaction with the screening procedures

How inconvenient did you find today's screening procedures?

Not Inconvenient 0	1	2	3	4	5	Very Inconvenient 6	Prefer not to answer
-----------------------	---	---	---	---	---	------------------------	----------------------

How difficult did you find today's screening procedures?

Not at all difficult 0	1	2	3	4	5	Very Difficult 6	Prefer not to answer
---------------------------	---	---	---	---	---	---------------------	----------------------

How satisfied were you with today's screening process?

Very dissatisfied 0	1	2	3	4	5	Very satisfied 6	Prefer not to answer
------------------------	---	---	---	---	---	---------------------	----------------------

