Appendix 6: VSQ-9

Patient Satisfaction Survey

Thinking about your visit with the physician/health care Professional you saw, how would you rate the following:

	Poor	Fair	Good	Very Good	Excellent
1. How long you waited to get an appointment					
2. Convenience of the location of the office					
3. Getting through to the office by phone					
4. Length of time waiting at the office					
5. Time spent with the physician/health care professional you saw					
6. Explanation of what was done for you					
7. Technical skills (thoroughness, carefulness, competence) of the physician/health care professional you saw					
8. The personal manner (courtesy, respect, sensitivity, friendliness) of the person you saw					
9. The visit overall					

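### At days 30, 60 and 90 the three satisfaction items still ask about today's screening, so as printed they do not measure satisfaction with linkage or the program

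*Combined protocol and SAP*

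**What the plan says.** Section 10.4.13 states the purpose of the scale: "A short 3 question satisfaction scale will be used to measure satisfaction with the screening and linkage process". On timing it says: "This will be asked at enrollment and the 30, 60, and 90-day follow-up assessments". Section 10.5.3 repeats the same purpose and schedule.

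Appendix 2 prints three items, each scored 0 to 6 with an option to decline. The first is "How inconvenient did you find today's screening procedures", the second asks in the same form about difficulty, and the third is "How satisfied were you with today's screening process". No separate wording for follow-up is given.

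Secondary Outcome 7 in Section 21.0 is program satisfaction. Its description reads "Program satisfaction at 30, 60 and 90-day follow-up", while its time-frame row gives 90 days only.

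Under Section 9.5 every follow-up assessment is a telephone call at day 30, 60 or 90. The list for those calls includes Section 4 of the ICAP form (HIV risk screening), the satisfaction questionnaire with a qualitative assessment, and the VSQ-9. The VSQ-9 in Appendix 6 opens with "Thinking about your visit with the physician/health care Professional you saw". Section 12.2 gives it a different timetable: "VSQ-9 study visit questionnaires collected at 30 and 90-day follow-up". Section 10.5.4 gives no timing.

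Section 11.1.2 names no analysis of satisfaction. Section 11.1.1 summarizes ordinal variables as frequencies and percentages.

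**The concern.** The scale is meant to cover two things, screening and linkage, but its items cover only the first. At enrollment this does little harm, because screening has just taken place. At follow-up the items refer to an event that is either absent or is something other than what the protocol intends.

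The follow-up scores matter most for comparing the arms. Behavioral screening precedes consent and randomization (Section 9.1), and Section 9.3 describes the enrollment assessments before it mentions randomization. An answer about ED screening therefore rates a step that is the same in both arms. Whatever the arms differ in, namely the immediate start, the starter pack and the course of linkage, comes later, and no item asks about it.

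Section 17.2 describes the trial as focused on feasibility and acceptability, and Aim 1b wants summary statistics on key measures for planning a definitive trial. An acceptability score whose reference is unclear would be carried into that planning.

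**Working it through.** The plan states no figure on this point, so there is none to reproduce. The check compares the texts and adds one small scoring calculation.

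**1. Stated construct against printed items.** Sections 10.4.13 and 10.5.3 name screening and linkage. In Appendix 2, 3 of 3 items refer to screening done today, and 0 of 3 mention linkage, the starter pack or PrEP care.

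**2. What the words can mean on a call.** There are three plausible readings:

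| Reading at day 30, 60 or 90 | Part of the ED program? | About linkage? |
|---|---|---|
| ICAP Section 4 risk questions just asked by phone | No | No |
| The telephone call as a whole | No | No |
| The ED visit 30 to 90 days earlier | Yes | No |

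None of the three gives satisfaction with linkage. Participants may also differ in which reading they choose, so a difference between arms or between time points could not be attributed to one thing.

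**3. Does the VSQ-9 fill the gap?** Its items rate a provider visit, including the wait for an appointment, reaching the office by phone, and the location. For a participant who has had such a visit, these touch on linkage. For one who never linked, there is nothing to rate. Linkage is an event after randomization that the intervention may affect, so the people able to answer need not be comparable between arms.

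**4. VSQ-9 schedule.** Section 9.5 implies days 30, 60 and 90; Section 12.2 says days 30 and 90. The disagreement concerns day 60 only.

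**5. Outcome 7 time frame.** Section 21.0 gives 90 days in one row and 30, 60 and 90 days in the next.

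**6. Item direction.** On items 1 and 2, 0 is the best answer and 6 the worst; on item 3, 0 is the worst and 6 the best. *If* the items were summed, which the plan does not say:

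- Raw sum = item 1 + item 2 + item 3. Best answers: 0 + 0 + 6 = 6. Midpoint: 3 + 3 + 3 = 9. Worst answers: 6 + 6 + 0 = 12.
- With items 1 and 2 reversed: (6 − item 1) + (6 − item 2) + item 3. Best: 6 + 6 + 6 = 18. Midpoint: 3 + 3 + 3 = 9. Worst: 0 + 0 + 0 = 0.

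An unreversed sum would rank the most satisfied pattern below the least satisfied one. Items reported singly are unaffected.

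**The case against.** The best defense is that Outcome 7 does not name the three-item scale as its only measure. Section 9.5 lists a qualitative assessment and the VSQ-9 beside it, the VSQ-9 is visit-specific by design, and all of this concerns an exploratory outcome in a pilot. Much of that stands, and it rules out several stronger readings that a reader might infer.

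- *The calls contain no screening.* They do: ICAP Section 4 is on the follow-up list. What is not repeated is the ED screening. The fault is ambiguity, and the phone risk questions add to it.
- *Outcome 7 cannot be measured at all.* The documents do not support this. The VSQ-9 gives information on access among those who linked, and a qualitative assessment is listed. Section 9.3 places that assessment in Appendix 2, where the available text shows only the three rating items. Because that text is incomplete, I draw no conclusion from it.
- *Satisfaction scores will come out reversed.* No total is planned. Under the default in Section 11.1.1 the items would be tabulated one by one, and direction does no harm.
- *The VSQ-9 would be answerable by 20 against 32 participants.* That comes from one row of the illustrative table in Section 11.1.3 (0.50 × 40 = 20; 0.80 × 40 = 32). The rows run from 20 against 22 (0.55 × 40) to 20 against 34 (0.85 × 40). More importantly, the table concerns retention at 90 days. Someone who attended once and then left care could still rate that visit, so retention does not give the number able to answer.
- *The schedule conflict invalidates the VSQ-9.* It decides only whether day-60 data exist.

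The defense does not supply follow-up wording for the scale. It also does not give participants who never linked a structured item on linkage that they can answer.

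**Conclusion.** The point holds in a limited form. The three-item scale, as printed and scheduled, does not measure satisfaction with linkage or the program at days 30, 60 and 90, although the protocol says linkage is part of what it measures. The VSQ-9 covers part of the gap, for those with a provider visit only, and its day-60 administration is contradictory. The Outcome 7 time frame also needs to be made consistent.

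This is a minor matter. It affects one exploratory secondary outcome; the primary outcome and the sample size are untouched. The conclusion assumes that the Appendix 2 items are read out on the calls as printed, since no other version is given. The remark on item direction matters only if a total is ever formed.

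**What to change.** - **Wording.** Keep the present items at enrollment. At days 30, 60 and 90 ask about linkage to PrEP care and follow-up since the ED visit, for example: *How satisfied have you been with the process of being linked to PrEP care since your Emergency Department visit?* Add matching items on inconvenience and difficulty. Both arms receive facilitated linkage, so everyone reached by phone can answer, whether or not they attended a visit. The ED visit should be the starting point; counting from the last study contact would miss linkage completed before day 30 when the items are asked at days 60 and 90.
- **Scoring.** State in Section 11.1.2 that the items are reported singly, or that items 1 and 2 are reverse-coded if a total is ever formed.
- **VSQ-9.** Report the number answering by arm, and label the result as satisfaction among those with a provider visit.
- **Consistency.** Use one VSQ-9 schedule in Sections 9.5 and 12.2, and one time frame for Outcome 7 in Section 21.0.

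The cost is a minor questionnaire amendment and a few lines of analysis text. The drawback is that enrollment and follow-up items would no longer be identical, so change from enrollment would not be reported. Little is lost, because with the present wording the two occasions need not refer to the same thing.

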10.4.14 CDC Sexual Behavior Questions

A comprehensive sexual risk assessment for HIV and other STIs. This measure will be completed at enrollment.

10.4.16 Attitudes toward Pre-Exposure Prophylaxis Scale (APS)

A brief assessment of knowledge and attitudes regarding PrEP. This assessment will be completed at enrollment and each follow-up visit.

10.5 Follow-Up Assessments

10.5.1 Attitudes toward Pre-Exposure Prophylaxis Scale (APS)

A brief assessment of knowledge and attitudes regarding PrEP.

10.5.2 Section 4 of ICAP "Screening for Substantial Risk of HIV"

Section 4 focuses on screening for substantial HIV risk.

10.5.3 Satisfaction Scale

A short 3 question satisfaction scale will be used to measure satisfaction with the screening and linkage process. This will be asked at enrollment, 30, 60, and 90 days post enrollment.

10.5.4 Visit specific satisfaction questionnaire (VSQ-9)

The VSQ-9 is a visit-specific satisfaction instrument adapted by the American Medical Group Association from the Visit Rating Questionnaire.

10.5.6 Guidelines Regimen Information Program (GRIP) guide

The GRIP measure is a validated instrument to assess medication compliance. This will be asked at each follow-up visit.

10.5.7 STAR*D PRISE

The STAR*D PRISE measure is a validated instrument designed to measure side-effects of common antidepressant medications but has been used widely as a general measure of medication side-effects. This will be administered at each follow-up assessment for those patients taking PrEP.

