Laboratory abnormalities will be addressed using standard ED clinical protocols. Patient with critical values will be asked to return to the ED for repeat evaluation and laboratory testing. Patients with abnormal values (HBV+ or elevated eCrCl) will be referred for out-patient evaluation. If a patient is found to have a clinical contraindication for PrEP their study participation will end.

Enrolled participants will also be asked to complete a number of validated and study team developed measures including:

- 1) Locator form with additional demographics (Appendix 1)
- 2) Satisfaction questionnaire and qualitative assessment (Appendix 2).
- 3) Attitudes towards PrEP Scale (Appendix 3)
- 4) CDC Sexual Behavior Questions (CSBQ) (Appendix 4)

to ED discharge all patients will receive a referral to an out-patient PrEP provider. Referrals are made through the Institute of Advanced Medicine (IAM) PrEP Warm Line, the IAM REDCap referral system, or via [contact]. Patients will also be asked to sign an Authorization for Release of Medical

Information. The medical release form is needed to confirm clinic follow-up for patients not receiving their follow-up care within the Mount Sinai Health System.

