Patients will be instructed at the time of discharge that they will be contacted by a member of the PrEP Warm Line to schedule follow-up with a PrEP provider. The decision to start PrEP for those not randomized to the iPrEP arm or to stop or continue PrEP for those randomized to the iPrEP arm will be a decision made by the patient in conjunction with their PrEP provider. The ED clinical team will be available to assist patients should have they have any concerns or problems before that linkage occurs. For those randomized to the iPrEP arm if they have any side-effects within the first 14-days of starter pack use they will contact the study team and a decision to continue or stop PrEP will be made after a discussion between the patient and the PI. All patients enrolled in the study will receive standard PrEP counseling which includes information about the need for frequent HIV testing and risk reduction strategies. The importance of follow-up with the PrEP provider will be stressed. We do not anticipate the need for any re-testing (HIV, LFTs, eCrCL) by the study team after ED discharge. These tests are not typically recommended until the patient has been on PrEP for at least 30 days and sometimes not until 90-days. All recommended follow-up testing will be the responsibility of the clinical PrEP provider.

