12.4 Protections against Risk

Investigators will make all efforts to minimize the physical, psychological, privacy and confidentiality risks to human subjects.

Physical Risks: In regard to screening for study entry, patients' discovered to have a clinical/laboratory contraindication for PrEP will be informed and educated by the PI regarding the reason for their ineligibility. Clinical/laboratory abnormalities will be addressed using standard ED protocols. Patients with a primary care provider will be referred back to their doctor for further management. For patients without a primary care provider follow-up will depend on the specific exclusion criteria. Patients with decreased eCrCL will be referred to out-patient nephrology. Patients found to have HBsAg+ will be referred to out-patient Hepatology. Patients found to be HIV+ will be immediately linked to care at Peter Krueger Clinic as per standard ED protocols. Patients found to be pregnant will be referred to out-patient Obstetrics and Gynecology.

All patients initiated on PrEP in the ED will be monitored by the study team for the first 14-days (the duration of the starter pack) or until linked to their outpatient PrEP provider. While we will not be dictating out-patient clinical care we expect that patients will be managed as recommended in the US Public Health Service Pre-Exposure Prophylaxis Clinical Practice Guidelines. This includes repeat HIV testing every 3-months, repeat pregnancy testing for women who may become pregnant, STI testing for sexually active persons with signs or symptoms of infection and eCrCL monitoring (every 6-months).

Psychological Risks: Patients may suffer from anxiety and discomfort at any point during the study. This could be the result of learning that they have one of the medical exclusion criteria or PrEP initiation or a sexually transmitted infection. The RAs will undergo extensive training with the New York City Department of Health and Mental Hygiene (NYC DOHMH) to learn the appropriate counseling skills to address patients concerns. In the event that a RA needs additional assistance they will reach out to the Principle Investigator or social workers from the Emergency Department.

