To maximize retention we will use a Locator Form to collect the study participants current address, email address, phone numbers and, with consent, private social media information. In order to facilitate linkage and follow-up, we will also collect similar information for friends and family who know how to reach the patient. All follow-up assessments will be conducted at 30, 60, and 90 from PrEP initiation. All follow-up assessments will be conducted by telephone. Patients will be mailed an appointment reminder and receive a phone call a week and a day before their scheduled assessment. Patients who miss one or more than one follow-up assessment will continue in the study so long as it is within 90 days of their enrollment.

We will provide a \$25 cash incentive for all participants to complete their enrollment, 30, 60 and 90-day follow-up assessments.

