2. Medications at the time of event: Yes No Unknown

Be sure to assess for dosage and date of last dose for the study medication, and any prior/concomitant medications as needed.

Medication (Generic Name)	Indication

3. Treatments for the event: Yes No Unknown

Treatment	Indication	Date Treated (mm/dd/yyyy)

4. Labs/tests performed in conjunction with this event: Yes No Unknown

Lab/Test	Findings	Date of Test (mm/dd/yyyy)

5. Follow-up:

Include labs/test results as they became available, clinical changes, consultant diagnosis, etc.

Comments:

Study staff completing form:

Date completed:

Patient ID

Date

 / /
MM DD YYYY

Level

Week in
level

Please indicate all symptoms you have experienced in the past week. These symptoms may or may not have been caused by your treatment.

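### As 10.5.7 is written, the PRISE side-effect form cannot describe symptoms during the 14-day starter pack or in anyone who stops PrEP before day 30 and does not resume

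*Combined protocol and SAP*

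**What the plan says.** Section 10.5.7 sets out who gets the form and when: "This will be administered at each follow-up assessment for those patients taking PrEP". The form, printed after the adverse event forms in Appendix 10, opens with "Please indicate all symptoms you have experienced in the past week". Section 9.5 fixes the calls: "Follow-up assessments will occur at 30, 60, and 90 days post enrollment". Its list of follow-up assessments includes PRISE as item 6, with no limit to PrEP users. Section 16.0 counts the calls differently: "All follow-up assessments will be conducted at 30, 60, and 90 from PrEP initiation"; 12.2 also counts from initiation.

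The enrollment measures in 9.3, introduced by "Enrolled participants will also be asked to complete a number of validated and study team developed measures including", are four in number, and PRISE is not among them.

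For the starter-pack period, 9.3 relies on the participant: "if they have any side-effects within the first 14-days of starter pack use they will contact the study team". Section 12.4 adds: "All patients initiated on PrEP in the ED will be monitored by the study team for the first 14-days", or until linkage to the outpatient provider. It names no form and no contact schedule.

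**The concern.** PRISE is the only symptom checklist in the plan. Three rules act together: current users only, one week of recall, first use at day 30. The starter pack is what separates the iPrEP arm from control, yet the checklist never looks at the days on which it is taken. The restriction to current users also selects people who tolerated the drug well enough to continue.

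The stake is what the pilot passes on. Aim 1b (section 4.0) is to supply data for planning a definitive trial. A table of PRISE symptoms among continuing users could be read there as the side-effect profile of ED-started PrEP, when it leaves out the early exposure and the early stoppers.

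**Working it through.** The plan states no figure on this point, so there is none to reproduce. The check is one of time windows.

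**Inputs.** Recall is 7 days (PRISE form). Calls are on days 30, 60 and 90 (9.5). The first iPrEP dose is on day 0, in the ED (9.3). The pack lasts 14 days (9.3, 9.8, 12.1.2). Controls are to start within 14 days of the ED visit (7.1, 20.0). The form is due for patients taking PrEP (10.5.7).

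**1. Windows.** Each runs from call day − 7 to call day: days 23–30, 53–60 and 83–90.

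**2. Overlap with the pack.** The pack occupies days 0–14, so the overlap is 0 days in all three windows. The gap before the first window is 23 − 14 = 9 days. In the iPrEP arm enrollment and initiation coincide, so the choice between 9.5 and 16.0 changes nothing here.

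**3. Who gets a form, under 10.5.7.**
- Stops before day 30 and does not resume: never.
- Stops between days 30 and 60: once at most.
- Stops between days 60 and 90: twice at most.
- After any stop: none, unless PrEP is resumed.

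**4. Stage of exposure.** Suppose a control starts on day s after enrollment. If calls count from enrollment, the day-30 form covers on-drug days 23 − s to 30 − s:
- s = 0: days 23–30
- s = 7: days 16–23
- s = 14: days 9–16

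The iPrEP arm is asked about days 23–30. If calls count from initiation, both arms are asked about days 23–30 and the difference vanishes.

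**5. How many would not be due a form at day 90.** The documents give no rate of stopping for side effects. The only usable figures are those in 11.1.3, which takes retention in care as PrEP use with 40 per arm. Control: 40 × (1 − 0.50) = 20. iPrEP: from 40 × (1 − 0.85) = 6 to 40 × (1 − 0.55) = 18. These are people not using PrEP for any reason, including controls who never started. They show how far the user restriction can reach, not how often side effects cause stopping.

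**6. Other routes for the same information.**
- 9.3: depends on the participant making contact.
- 12.4: monitoring for 14 days or until linkage, with no instrument or schedule.
- 17.2: the reason for discontinuation is asked of patients who wish to stop; someone who stops silently may not be asked.
- 18.4 with Appendix 10: adverse events are elicited at each follow-up assessment, so first at day 30. The form has onset date, severity, causality and, for events judged possibly drug-related, the action taken, including permanent stopping.
- 18.9: an end-of-medication visit for voluntary withdrawal in the first 14 days in the iPrEP arm; the outcomes to be documented are not defined.

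These record events. None gives a fixed list of symptoms asked of everyone.

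**7. A further loss.** Section 17.2 names intolerable side effects as an indication for stopping and says that iPrEP patients in whom such concerns arise during the pack are withdrawn from the study. They may then have no day-30 call, and so neither PRISE nor the 18.4 elicitation.

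**The case against.** A reader might infer that the trial loses everyone who stops because of side effects. The documents do not support that. Someone who stops after day 30 is due a PRISE at one or more earlier calls. Adverse event elicitation under 18.4 is not limited to users and has no one-week limit, so the day-30 call can reach back to day 0. The adverse event form can record a permanent stop, 17.2 asks the reason, and 18.9 adds a visit for early voluntary withdrawal in the iPrEP arm. The gap is in PRISE, not in all safety data.

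A reader might also take tolerability to be a main safety result of the pilot. It is not among the aims in 4.0, the secondary aims in 7.2 or the outcomes in 21.0, and 11.1.2 plans no PRISE analysis and no comparison of it between arms. Section 17.2 describes the trial as one of feasibility and acceptability of an approved drug.

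The user restriction itself is not settled, since 9.5 omits it. The difference between arms in stage of exposure depends on which visit anchor applies. Partial coverage of the follow-up period (3 × 7 = 21 of 90 days, 23%) is a property of any past-week form used three times and is no defect in itself.

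All of this stands and narrows the point. It does not remove it: the other routes supply no checklist, the 14-day monitoring has no form, and the pack lies outside every PRISE window even if the unrestricted wording of 9.5 governs.

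**Conclusion.** The point holds for PRISE alone. As 10.5.7 is written, PRISE covers 0 of the 14 pack days, is never given to those who stop before day 30 and do not resume, and is not repeated after a later stop. Side effects in these people rest on event reports and stated reasons. A PRISE summary would therefore tend to understate side effects; the size of the understatement cannot be derived from the documents.

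The timing result rests on a day-0 first dose in the iPrEP arm and calls made on their nominal days. The result on early stoppers rests on 10.5.7 prevailing over 9.5. The documents do not support saying that side-effect discontinuations go unrecorded. The change is worth making because it is cheap and the pilot's data are meant to inform a larger trial.

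**What to change.** 1. Reconcile 9.5 with 10.5.7: at each call, give PRISE to every participant in either arm who took any PrEP dose since the last contact. Those who have stopped answer for their last week on PrEP.
2. Complete PRISE once during the 14-day monitoring already planned in 12.4, and at the 18.9 end-of-medication visit where that takes place. The first of these also gives a chance to reach patients withdrawn under 17.2 before they leave.
3. Report PRISE over all participants ever exposed, with days since first dose, beside discontinuations from the adverse event form and reasons for stopping, by arm.
4. Reconcile the two visit anchors, enrollment (9.5) and PrEP initiation (12.2, 16.0).

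The cost is a wording and form amendment, a few more minutes on planned calls, and one form within planned monitoring. For stoppers, recall is longer and the question departs slightly from the form's past-week wording. One form during the pack still sees at most 7 of its 14 days. It has no counterpart at the same point in the control arm, so it should be reported descriptively. No treatment rule changes.
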